**Splanchnic Nerve Block for Therapy of Chronic Heart Failure (Splanchnic III)**

**Clinicaltrials.gov number: NCT04575428**

**Duke IRB number: Pro00103788**

**Date: May 1th 2023**

## Research Abstract

### Please type your Research Abstract here:

The Research Abstract should summarize the main points of your study in one paragraph. The following guidelines may help you:

1. Purpose and objective (1-2 sentences)
2. Study activities and population group (2-4 sentences)
3. Data analysis and risk/safety issues (1-2 sentences)

Splanchnic vasoconstriction may contribute to decompensation of chronic heart failure (HF) via volume redistribution from the splanchnic vascular bed to the central compartment. This is a sympathetically mediated reflex and can be interrupted through a splanchnic nerve block (SNB). We hypothesize that interruption of the efferent/afferent innervation of the splanchnic vasculature will decrease cardiac congestion and improve renal function in patients presenting with HF.

We have already obtained preliminary safety and efficacy data in acute and chronic heart failure patients with temporary (<24 h) SNB. Now we would like to apply a prolonged SNB in chronic heart failure patients using a long acting agent.

## Research Summary

### State your primary study objectives

1. We will determine if splanchnic nerve blockade decreases cardiac preload as measured by invasive hemodynamics.
2. We will determine if splanchnic nerve blockade will improve invasive hemodynamics during exercise.
3. We will determine if splanchnic nerve blockade improves symptoms of shortness of breath.

### State your secondary study objectives

N/A

### Please select your research summary form:

Standard Research Summary Template

This is the regular (generic) research summary template which is required for all regular applications (unless your protocol fits under the other research summary templates in this category). Use of these instructions is helpful for ensuring that the research summary contains all necessary elements.

## Standard Research Summary

### Purpose of the Study

- Objectives & hypotheses to be tested

1. We will determine if splanchnic nerve blockade decreases cardiac preload as measured by invasive hemodynamics.
2. We will determine if splanchnic nerve blockade will improve invasive hemodynamics during exercise.
3. We will determine if splanchnic nerve blockade improves symptoms of shortness of breath.

## Background & Significance

- Should support the scientific aims of the research

Heart failure (HF) is a leading cause of morbidity and mortality, affecting more than 6 million adults in the US alone. Cardiovascular congestion with resultant limitation in physical activity is the hallmark of chronic and decompensated HF. While it is well-accepted that the extent of fluid volume congestion is closely associated with clinical outcomes, the concept of fluid and salt overload as the primary drivers of symptomatic decompensation (with resting or exercise-induced dyspnea) has been challenged. Notably, about 50% of patients gain only minor weight (<2pounds or <2kg based on the study) in the days prior to a hospitalization. Additionally, intracardiac filling pressures in patients with HF commonly start to increase before any significant weight changes occur preceding an admission for clinical decompensation. In our own analysis of the ASCEND-HF trial, 26% of patients had no weight loss (+/-1kg change) and 8% actually experienced weight gain (31kg) during a HF hospitalization, suggesting that net volume loss is not necessary for symptomatic relief. **Taken together, an increase in central filling pressures occurs in many cases in the absence of weight gain or total body volume increase, which lead us and others to suggest a contribution of volume redistribution to the mechanism of cardiac decompensation**

In chronic HF, cardiopulmonary congestion is the main determinant of exercise intolerance, which manifests itself as exertional dyspnea and/or fatigue. Many HF patients have normal hemodynamics at rest, but there is growing evidence of profoundly abnormal hemodynamic response to exercise characterized by rapid and marked elevation in filling pressures. Exercise-induced intra-cardiac decompensation, whether driven by fluid overload or volume redistribution, in most cases is only an intermittent phenomenon as pressures return to baseline values during recovery.

The abdominal compartment has been implicated as a key contributor to the complex pathophysiology of HF given that it is the main storage compartment of intravascular blood volume. The highly vascular organs such as the liver, spleen and bowel are able to "store" or "recruit" large blood volumes within minutes in and out of the splanchnic vascular compartment. Animal and human data indicates that these blood shifts can significantly alter cardiac and central vascular hemodynamics. **The main regulatory system for the splanchnic vascular capacitance ("storage-space") are post-ganglionic sympathetic fibers originating from the celiac plexus which control arterial and venous vascular tone.** These post-ganglionic sympathetic fibers in the celiac plexus receive input from pre-ganglionic sympathetic fibers travelling via splanchnic nerves. **Activation of splanchnic nerves results in vasoconstriction and reduces splanchnic capacitance, therefore recruiting blood volume into the central circulation. In HF, a reduced splanchnic vascular capacitance could be the mechanism underlying symptoms of exercise intolerance and could predispose to rapid decompensation with external fluid intake or retention (Figure 1).** A compromised vascular reservoir is likely unable to buffer shifts of fluid and actively contributes to the acute or chronic expulsion of fluid from the splanchnic vascular compartment to the central thoracic compartment. The redistribution of blood volume into the central circulation may lead to a sudden rise in pulmonary and left-sided cardiac pressures in HF. This makes the splanchnic vascular compartment an attractive target in HF.

**Prior Evidence:** Mounting evidence questions the notion that congestion is merely the result of external volume overload or volume retention. Supportive evidence is provided by blood volume analysis using the I-labeled human serum albumin indicator-dilution technique. Using this technology, studies found that chronic HF patients with persistent symptoms are in 35% of cases hypovolemic or euvolemic and the same was even true for patients admitted for decompensated HF (34%). The heterogeneity of clinical presentation suggests the presence of an alternate mechanism to explain increased filling pressures at rest or with exercise despite a lack of fluid retention.

**Effective measures to decrease vascular congestion acutely or chronically remain an unmet clinical need. We recently identified the splanchnic nerves as potential contributors to the pathophysiology of HF and we proposed that a heightened splanchnic sympathetic tone contributes to cardiac decompensation and a short-term interruption of the splanchnic nerve signaling would reverse the process and thus alleviate HF sign and symptoms in select patients with acute and chronic HF.** We first showed that splanchnic nerve stimulation results in acute hemodynamic changes, with a decrease in splanchnic vascular compliance and increase in cardiac preload. HF is characterized by a heightened global sympathetic tone, yet untargeted pharmacological reduction in sympathetic tone can be insufficient to result in effective splanchnic vasodilation and be detrimental due to unintended cardiovascular effects. Consequently, a targeted reduction of the splanchnic sympathetic tone in chronic HF could provide a therapy for patients with cardiopulmonary congestion at a resting state or state of activity.

Our preliminary proof-of-concept work in patients with acute decompensated and chronic HF showed promise for the concept of splanchnic nerve modulation in HF (**Figure 2**). In a series of two small first-in-human studies for acute decompensated HF (N=13) (Late-Breaker at ESC-HF 2018, Vienna, Austria, NCT02669407) and chronic HF (N=17) (Young Investigator Competition, ESC-HF 2019, Athens, Greece, NCT03453151), we found that a splanchnic nerve block (SNB) with lidocaine (90 min duration of action) and ropivacaine (24 hours duration of action) acutely **reduced resting and exercise-induced** intra-cardiac filling pressures, associated with improved patient symptoms and functional capacity.

Our two proof-of-concept studies and the well-established safety profile of permanent splanchnic nerve blockade in patients with intractable abdominal pain (e.g., due to pancreatitis or cancer) provide the foundation for our study. A body of literature (>3,000 published cases) on non-HF patients suggests that the side effects of permanent splanchnic nerve blockade (surgical or interventional via alcohol injection) are restricted to 48-h post procedure. Most common side effects include orthostatic hypotension (80%) followed by gastrointestinal symptoms (60%). Interestingly, transient orthostatic hypotension due an increase in splanchnic vascular storage capacity, is clinically prevented by aggressive pre-procedural hydration. Historically (1930-1950's) surgical denervation of splanchnic nerves has also been applied in form of the so-called splanchnicectomy for treatment of uncontrolled hypertension. While it was shown to be effective to reduce sympathetic tone and reduce blood pressure, the discovery of antihypertensive medications made this surgical procedure obsolete. Long-term pharmacological blockade of the celiac plexus/splanchnic nerves with Botulinum toxin (BTX) has been previously reported to be safe and effective in a case of refractory hypertension. Finally, our group has extensive experience with neuromodulation which includes the application of BTX to epicardial fat pads for prevention of post-operative atrial fibrillation and stellate ganglion blockade for ventricular arrhythmias. **Together, published evidence and our data indicates the potential importance of splanchnic nerve modulation as a treatment for HF, providing a strong scientific premise for further investigation in this field.**

## Design & Procedures

- Describe the study, providing detail regarding the study intervention (drug, device, physical procedures, manipulation of the subject or the subject's environment, etc.). Discuss justifications for placebo control, discontinuation or delay of standard therapies, and washout periods if applicable. Identify procedures, tests and interventions performed exclusively for research purposes or more frequently than standard of care. Include alternative therapies, concurrent therapies discontinued per protocol, risk benefit ratio, and use of tissue/specimens. Discuss monitoring during washout periods if applicable. Include brief description of follow-up, if any.

**Study design.** The present study will be a prospective open-label pilot study to help establish feasibility, safety and enable dose finding for BTX. The schedule of events is presented in **Figure 3**. Following a baseline invasive (right heart catheterization) cardiopulmonary exercise testing (CPX) patients will undergo unilateral celiac plexus block (**Figures 2 and 4**), followed by repeat hemodynamic testing in the following 90 minutes. Repeat CPX (with and without hemodynamic testing) will occur at 2, 4, 8 weeks. A 12 month phone call to investigate vital status, HF hospitalizations will conclude the study. Functional testing at baseline and follow up will be supplemented by a series of minimally invasive and non-invasive measures of static and dynamic blood volume distribution (radionuclear plethysmography, bioelectrance, hepatic vein ultrasound), congestion parameters (biomarkers, BVA), autonomic nervous tone (catecholamines,

baroreflex, and heart rate variability) and symptom questionnaires (Likert and Visual Analog scale). Given high volume of patients and right heart catheterizations (>1,000 per year) and our experience with enrolling patients in the preliminary studies, we anticipate to complete recruitment within 2 years.

Figure 2. Splanchnic Nerve Block Procedure (A) and Prior Data of Nerve Blockade in Acute (B) and Chronic Heart Failure (C). \* indicates p<0.05

[figure not shown]

Figure 3. Study Flow

[figure not shown]

Figure 4. Study set-up: Invasive hemodynamic testing

[figure not shown]

Table 1: Schedule of events (CS, clinical study; SOC, standard of care/clinical)

Required Assessment	Pre-Procedure (Day 1)	Baseline (Intra-Procedure)	Block	Post-Block Procedure	48 Hour	Week 1	Week 2	Week 4	Week 8	Month 6	Month 12
Vitals (BP, HR, RR, SpO 2 , weight)	X (CS)			X(CS)		X(CS)	X(CS)	X(CS)			
Orthostatic vitals	X(CS)			X(CS)		X(CS)	X (CS)	X (CS)			
Non-Invasive Testing*	X(CS)			X(CS)		X(CS)	X (CS)	X (CS)			
Pregnancy test	X (SOC)										
Labs: BMP (SOC), pro-BNP (CS), CA-125 (CS), urine sodium (CS),	X (CS /SOC)			X (CS /SOC)		X (CS /SOC)	X (CS /SOC)	X (CS /SOC)			
Labs Renin, Angiotensin II, Vasopressin, Plasma Catecholamines	X (CS)			X (CS)		X (CS)	X (CS)	X (CS)			
				X(CS)	X(CS)				X(CS)	X(CS)	

Dyspnea and EQ-5D-3L Questionnaires	X (CS)		X(CS)		X(CS)	X (CS)	X(CS)		
Six minute walk test	X (CS)		X(CS)		X(CS)	X (CS)	X(CS)		
Blood volume - Daxor	X (CS)					X (CS)			
Heart rate variability	X (CS)	X (CS)	X (CS)		X (CS)	X (CS)	X (CS)		
Right Heart Cath (RHC)		X (CS, SOC)				X (CS)			
Scintigraphy	X (CS)					X (CS)			
Invasive CPX (peak VO2)		X (CS)				X (CS)			
CPX (peak VO2)					X (CS)		X (CS)		
Echocardiogram		X (CS)	X (CS)		X (CS)	X (CS)	X (CS)		
Renal ultrasound (to be done by [name])	X (CS)		X (CS)		X (CS)	X(CS)	X (CS)		
Splanchnic nerve block			X (CS)						
Phone Call				X (CS)	X (CS)			X (CS)	X (CS)

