**Nerve Block Procedure.** The unilateral, left-sided, temporal bilateral celiac plexus block will be performed by the interventional pain specialty team in the catheterization laboratory, with continuous hemodynamic monitoring similarly to our previously published experience. The celiac plexus block will be performed under fluoroscopic guidance in the posterior chest wall (vertebral space L1) to guarantee maximal safety (**Figure 2**). We will use a mix of 3 ml of lidocaine 1.55 with 1:10000 epinephrine, 10 ml of 0.5% ropivacaine and up to 1.5 U/kg of BTX Type A. Lidocaine with epinephrine is used for procedural

safety to exclude intravascular injection. In the present study we will start at a lower dose of the BTX (dose finding). We will plan to increase dose or decrease per Kg unit doses for Botox based on 4 week assessment.

The dosing up titration scheme (Scenario 1) is as following:

1. The 1st and 2nd subject receiving the block splanchnic procedure - 75Units of Botox, (not more than 1.5 Units/kg) follow up at 2 weeks with CPX and 4 weeks with invasive CPX and 8 weeks with CPX
2. The 3rd and 4th subject receiving the block splanchnic procedure - if prior dose tolerated, no safety issues at 4 weeks than proceed with dose increase to: 100Units of Botox, (not more than 1.5Units/kg) follow up at 2 weeks with CPX and 4 weeks with invasive CPX and 8 weeks with CPX
3. The 5th and 6th subject receiving the block splanchnic procedure - Scenario 1: if prior dose tolerated, no safety issue and satisfactory efficacy at 4 weeks than patient 5/6 will get injection of 100Units of Botox again (not more than 1.5Units/kg) with follow up at 2 weeks with CPX and 4 weeks with invasive CPX and 8 weeks with CPX Satisfactory efficacy is defined as >25% reduction with exercise wedge pressure  
Scenario 2: if prior dose tolerated, no safety issue and efficacy not satisfactory at 4 weeks than patient 5/6 will get injection of 125Units of Botox (not more than 1.5Units/kg) with follow up at 2 weeks with CPX and 4 weeks with invasive CPX and 8 weeks with CPX.

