  6. Heart Rate Variability: The WHOOP strap 3.0 will measure heart rate and heart rate variability and will be worn for approximately one hour.
3. 6 minute walk test to measure your exercise capacity and endurance.
4. Questionnaires about the subject's feeling about their shortness of breath and breathing at rest
5. Cardiopulmonary (CPX) Testing: Exercise testing with the subject using an upright bike. The subject will exercise at their maximum effort. The subject will be monitored for exercise intolerance, shortness of breath, or pain in the chest. The subject will wear a face mask to measure oxygen intake and carbon dioxide output.
6. MUGA Scan: non-invasive imaging method to evaluate the function of your heart. This scan will help determine more information about the health of the subject's cardiac ventricles and blood distribution.

Laboratory Tests:

1. Blood Volume Analysis: Administration of a small amount of plasma protein, albumin, containing a small amount of radioactive iodine (injected through the PIV). The radioactive iodine labeled albumin

protein (blood volume solution) will be administered through the PIV line. Blood samples will be withdrawn before administration of the blood volume solution and 12, 16 and 20 minutes after administration. The blood samples will be processed at the Duke Nuclear Laboratory using the Daxor Analyzer for further processing

2. Biomarkers: Blood samples will be taken before the procedure and after the procedure for analysis of NT pro-BNP (indication of worsening heart failure) and CA-125 (indication of inflammation).
3. Autonomic Nervous System regulators: Blood samples will be taken in the catheterization lab before and after the splanchnic block. The samples will be processed and sent out to labs that specialize in analyzing these samples for hormones angiotensin II, vasopressin, catecholamines, and metanephrines.

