### Data Analysis & Statistical Considerations

- Describe endpoints and power calculations. Provide a detailed description of how study data will be analyzed, including statistical methods used, and how ineligible subjects will be handled and which subjects will be included for analysis. Include planned sample size justification. Provide estimated time to target accrual and accrual rate. Describe interim analysis including plans to stop accrual during monitoring. Phase I studies, include dose escalation schema and criteria for dose escalation with definition of MTD and DLT.

[name] in the Duke Heart Center will be performing the statistics for the Splanchnic III study. We will perform descriptive statistics. Statistical comparisons will be made using t-tests for continuous outcomes and chi square or Fisher's exact test. Unless otherwise specified, a two-sided 0.05 level of significance will be used to declare change in pre-and post-procedure variables different.

There is no direct measure of technical success following attempted block of the splanchnic nerves. Procedural success to block the splanchnic nerves will be assumed in 70% of the cases based on the experience in splanchnic nerve blocks in patients with intractable cancer.

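### The objectives and the pre/post test name neither agent nor time point, so same-day local-anesthetic readings can meet objectives meant for the prolonged BTX block

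*Combined protocol and SAP*

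**What the plan says.** **Purpose.** The Research Abstract notes that blocks lasting under 24 hours have been studied already and gives the next step: "Now we would like to apply a prolonged SNB in chronic heart failure patients using a long acting agent". Design & Procedures describes an open-label pilot with BTX dose finding. No arm receives local anesthetic alone.

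**Injectate.** The Nerve Block Procedure paragraph under Testing procedures lists "3 ml of lidocaine 1.55 with 1:10000 epinephrine, 10 ml of 0.5% ropivacaine and up to 1.5 U/kg of BTX Type A". Study Interventions lists 12 cc of ropivacaine with Botox and mentions neither lidocaine nor epinephrine.

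**Timing.** Design & Procedures has the block "followed by repeat hemodynamic testing in the following 90 minutes". Background & Significance describes the earlier agents as "lidocaine (90 min duration of action) and ropivacaine (24 hours duration of action". The down-titration paragraph has ropivacaine working from about 15 minutes for 24 hours and BTX peaking at 2 weeks. It gives no onset time for BTX.

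**Earlier results.** Background & Significance reports two studies (N=13 and N=17) in which lidocaine and ropivacaine, without BTX, lowered filling pressures at rest and on exercise, "associated with improved patient symptoms and functional capacity".

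**Objectives and test.** The three primary objectives concern preload, exercise hemodynamics and dyspnea under splanchnic nerve blockade in general. Data Analysis & Statistical Considerations says that "a two-sided 0.05 level of significance will be used to declare change in pre-and post-procedure variables different". It names no primary endpoint and no visit.

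**Autonomic samples.** Study Interventions states: "Autonomic Nervous System regulators: Blood samples will be taken in the catheterization lab before and after the splanchnic block". Catecholamines and metanephrines are among the analytes.

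**The concern.** Every patient receives two blocks through one needle: a short one from the local anesthetic and a long one from BTX. The trial is about the long one, but a reading taken an hour after injection qualifies as post-procedure just as a week-4 reading does. Objectives 1 and 3, and objective 2 if the retest includes exercise, could then be declared met on a response the group has already described without BTX, even if BTX did nothing at weeks 2 to 8.

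This is separate from multiplicity. With a single variable and a single test, a same-day reading would still address a different drug from the one in question.

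A smaller issue of the same kind affects one blood sample. If the injectate contains epinephrine, the epinephrine measured just afterward is not a clean measure of the patient's own sympathetic activity.

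**Working it through.** **1. Which agent can act at which reading**

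| Reading | Time from injection | Inside the 15 min to 24 h ropivacaine window? |
|---|---|---|
| Repeat hemodynamics | up to 1.5 h | from 15 min on; 1.5/24 = 6.25% of the stated duration |
| Week 2 (stated BTX peak) | 14 × 24 = 336 h | no |
| Week 4 (invasive CPX) | 28 × 24 = 672 h | no |

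Table 1 also appears to place vitals, labs, the dyspnea questionnaire, walk test and echocardiogram after the block on the same day. Its layout is broken in the available text, so those positions are inferred. The right heart catheterization and invasive CPX rows show only two marks each, which read as baseline and one later visit. The same-day invasive reading therefore rests on the sentence in Design & Procedures, which does not say whether the retest includes exercise.

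**2. Whether the text confines the tests to later readings**

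- Objectives (Research Summary and Purpose of the Study): no agent, no time point.
- Data Analysis: pre versus post procedure, no time point. It adds that technical success has no direct measure and assumes 70% success, so it does not take up the acute response as a check.
- Nerve Block Procedure: the acute effect confirms the procedure, and dosing efficacy (more than a 25% fall in exercise wedge pressure) is judged at 4 weeks.

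Only the dosing text separates the two effects.

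**3. How often a same-day test succeeds when BTX does nothing**

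The documents give no total sample size, SD, effect size or power, so there is no figure to reproduce. N = 6 is the number of subjects named in the dosing scheme. N = 15 and the standardized local-anesthetic effect d (mean change divided by the SD of the change) are assumptions. For a two-sided paired t-test at 0.05:

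P(significant) = P(|T| > t₀.₉₇₅,ₙ₋₁), where T is noncentral t with n − 1 df and noncentrality d√n.

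The critical values are 2.571 (n = 6) and 2.145 (n = 15).

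| d | d√6 | N = 6 | d√15 | N = 15 |
|---|---|---|---|---|
| 0.5 | 1.22 | 17% | 1.94 | 44% |
| 1.0 | 2.45 | 51% | 3.87 | 95% |
| 1.5 | 3.67 | 83% | 5.81 | >99% |
| 2.0 | 4.90 | 97% | 7.75 | >99% |

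In a simulation of 40,000 trials per setting (same-day and week-4 changes correlated 0.5, mean week-4 change zero), the week-4 test was significant in about 5% for every d. If either time point may count, the N = 6 figures are 21%, 53%, 85% and 97%. With no effect at either time they fall to about 9%, against 1 − 0.95² = 9.75% for independent tests.

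**4. Epinephrine in the injectate**

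Reading 1:10000 as 1 g in 10,000 ml gives 0.1 mg/ml, and 3 ml × 0.1 mg/ml = 0.3 mg. This is an amount injected, not a change in plasma level. The draw time and clearance are not given, so the effect on the sample cannot be computed.

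**The case against.** The strongest reply is that the protocol already knows the difference. It assigns the acute effect a confirmatory role, takes dose decisions from the 4-week assessment, and nowhere says that same-day data will be the efficacy test. This stands, and it limits the point to the objectives and the analysis section. The visit schedule is not at fault.

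Second, a ropivacaine block is a splanchnic nerve block, so a same-day statement that blockade lowers preload would be true. It misleads only if taken as evidence for the prolonged block. It follows that the 17% to 97% are not false-positive rates. They are the power to detect an assumed real anesthetic effect, which would count toward the wrong question.

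Three stronger readings are tempting and not supported:

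- A reader might infer that BTX contributes nothing at 90 minutes because that is a tiny fraction of the 2 weeks to peak. A fraction of time is not a fraction of effect, and no onset is stated. Attribution to the local anesthetic is a reasonable inference from its stated window and the earlier results, not a documented fact.
- A reader might infer that the catecholamine results as a whole are spoiled. Only the post-block draw is affected. Catecholamines are supplementary measures, and later plasma catecholamine draws are scheduled. The epinephrine itself appears in one of two conflicting injectate descriptions.
- A reader might infer that later metanephrine values could replace the affected one. Metanephrines are listed only for the samples around the block.

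**Conclusion.** The point holds as a gap between the stated purpose and the text that defines the test. As written, day-of-block readings count as post-procedure and can satisfy the objectives without testing the prolonged BTX block. With zero BTX effect, a same-day test at N = 6 is significant in 17% to 97% of trials for d from 0.5 to 2.0, against about 5% at week 4. That range depends on the assumed d and on N = 6. The direction depends only on a real acute anesthetic effect, which the group's own earlier studies report.

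A reader might infer that a week-4 change would then prove a BTX effect. It would not: week 4 removes the local anesthetic as an explanation, but the study remains uncontrolled and open-label. The 5% figure assumes no mean change from any other source.

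The epinephrine part is a caution about one exploratory sample. It depends on which injectate description is correct, and on the assumption that injected epinephrine and its metabolite reach the sample; the documents describe no way to separate them from the patient's own.

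**What to change.** - State that objectives 1 to 3 concern the prolonged (BTX) block.
- In Data Analysis, test objectives 1 and 2 on baseline versus week-4 invasive hemodynamics. Test objective 3 on one named visit after the ropivacaine window, for example week 4, with the other visits supportive. Leaving a range of weeks would keep the choice of time point open.
- Report day-of-block changes separately, as acute local-anesthetic response and procedural confirmation.
- If the injectate contains epinephrine, do not interpret the post-block epinephrine or metanephrine value as endogenous sympathetic tone. Compare the later scheduled plasma catecholamine draws with the pre-block sample.
- Reconcile the two injectate descriptions (Nerve Block Procedure and Study Interventions). Also reconcile the 90-minute retest with the 60 minutes of post-block monitoring in Study Interventions and with Table 1.

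The cost is wording only, with no added visit, sample or patient. The downside is that the acute result, which may be the most favorable one, no longer supports the objectives.
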